The mean plasma concentration time profiles for efinaconazole and metabolites (H3 and H4) will be presented graphically for Days 28 and 29 in both linear and logarithmic scales. Individual subject plasma concentration time profiles for efinaconazole and metabolites (H3 and H4) will also be created.

Plasma PK parameters for efinaconazole and metabolites (H3 and H4) will be calculated using noncompartmental analysis. The PK parameters will be calculated for each subject using actual sampling times. The maximum plasma concentration (C_{max}) and time to C_{max} (T_{max}) will be taken directly from the data.

The following PK parameters will be calculated from the individual plasma concentrations on Days 28 and 29 when possible:

- C_{max} (observed peak drug [efinaconazole and metabolites] concentration)
- T_{max} (time at which C_{max} occurs)
- C_{min} (observed minimum drug concentration)
- AUC_{0-t} (area under the concentration-time curve from time 0 up to the sampling time corresponding to the last quantifiable concentration)
- AUC_{0-24h} (area under the concentration-time curve from time 0 through 24 hours [corresponding to the dosing interval])

Additional PK parameters may be calculated as appropriate.

The PK objectives will be considered met when approximately 16 evaluable subjects are treated under maximal use conditions through day 28 of the PK evaluation.

Sample size calculations:

Approximately 60 subjects will be enrolled and receive treatment with study drug. Approximately 20 of the subjects will be enrolled in the PK subset. These sample sizes were based on PK and clinical considerations; no formal sample size calculation was performed. The numbers of planned subjects are considered adequate for determining the safety profile and the PK parameters of efinaconazole in a pediatric population of subjects aged 6 to 16 years 11 months with mild to severe onychomycosis of the toenails.

3 Table of Contents

1	TITLE PAGE	1
2	SYNOPSIS	5
3	TABLE OF CONTENTS	13
4	LIST OF ABBREVIATIONS AND DEFINITIONS OF TERMS	17
5	INTRODUCTION	18
6	STUDY OBJECTIVES AND PURPOSE	19
7	INVESTIGATIONAL PLAN	19
8	SELECTION AND WITHDRAWAL OF SUBJECTS	27
8.1	Subject Inclusion Criteria	27
8.2	Subject Exclusion Criteria	28
8.3	Subject Withdrawal Criteria	30
9	TREATMENTS PLANNED	30
9.1	Methods of Assigning Subjects to Treatment Groups	30
9.2	Randomization and Blinding	31
9.3	Treatment Compliance	31
9.4	Treatment Administration	31
9.5	Concomitant Medications	32

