application technique for the study drug and provide the appropriate Subject Instruction Sheet with dosing instructions (ie, for non-PK or PK subjects), depending on whether the subject is enrolled in the PK subset. Record any AEs following the initial treatment application.

20. Record local skin reactions. Instruct the subject and their parent/legal guardian to report local skin reactions (if any) at each study visit.
21. Schedule the next study visit (Visit 3 [Week 4, Day 28]) in 28 days (\pm 5 days).

Note: (\pm 5 days) only applies to Non-PK subjects, PK subset only has a (\pm J day) visit window

- For subjects in the PK subset, Visit 3 (Week 4, Day 28) to Visit 3A (Week 4, Day 29) remind subjects not to apply study drug the night prior to their Visit 3 (Week 4, Day 28) visit.

11.1.3 Visit 3 (Week 4, Day 28 [\pm 5 days]), Visit 4 (Week 5 [\pm 5 days]), Visit 6 (Week 16 [\pm 5 days]), Visit 7 (Week 20 [\pm 5 days]), Visit 9 (Week 28 [\pm 5 days]), Visit 10 (Week 32 [\pm 5 days]), Visit 12 (Week 40 [\pm 5 days]), Visit 13 (Week 44 [\pm 5 days])

Visits are to be scheduled in reference to Visit 2 (Baseline).

The following procedures will be conducted at this visit:

1. Record any AEs (query subjects and their parents/legal guardians, "Are there any changes in your health since the last visit?").
2. Record local skin reaction scores reported by the subject and parent/legal guardian.
3. Review concomitant medications.
4. Clip the toenails.
5. Measure the target great toenail growth since the Baseline Visit (distance from proximal nail fold to transverse notch). If the most recently applied notch has grown out or has been clipped off, inscribe a new notch adjacent to the proximal nailfold.
6. Collect the diary and study drug bottle from the subject and/or their parent/legal guardian. Weigh the used bottle of the study drug. Record the number of missed doses from the subject diary and review compliance with the subject.
7. Conduct a urine pregnancy test on FOCBP subjects (discontinue any subject from the study who has a positive test result)
8. Obtain 1 bottle of study drug and weigh the bottle, complete the label and drug log, and dispense the bottle to the subject and their parent/legal guardian. Review the dosing instructions with the subject. (Subjects in the PK subset will not be dispensed study drug this day).
9. Dispense diary. (Subjects in the PK subset will not be dispensed a diary this day.)
10. Schedule the next study visit.

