Note: PK subjects exiting the study on Day 29 (consented to only the 4-Week trial), the following procedures will be conducted in addition to the procedures listed above.

11. Collect blood and urine samples for routine safety laboratory analysis (hematology, serum chemistry, and urinalysis). Process and ship the samples to the central safety laboratory per instructions provided in the laboratory manual.
12. Measure height and weight.
13. Conduct an abbreviated physical examination (excluding urogenital/reproductive systems).

For subjects in the PK subset at Visit 3 only:

- Collect a predose blood sample after all other study procedures are completed.
- Apply the study drug to all 10 toenails at the investigational center within 1 hour after collecting the predose blood sample.
- Collect postdose blood samples at approximately 2 hours (\pm 5 min), 4 hours (\pm 5 min), and 12 hours (\pm 15 min) after study drug application.
- Instruct the subject to return the following morning for their 24-hour blood sample (Visit 3A (Day 29). Subject will not dose on the evening of Day 28.

11.1.4 Visit 3A (Week 4, Day 29) - Additional Visit for Subjects in the PK Subset

The following procedures will be conducted at this visit:

1. Record any AEs (query subject "Are there any changes in your health?").
2. Record local skin reaction scores reported by the subject.
3. Review concomitant medications.
4. Collect a blood sample 24 hours (\pm 30 min) after study drug application at Visit 3.
5. Obtain 1 bottle of study drug and weigh the bottle, complete the label and drug log, and dispense the bottle to the subject and their parent/legal guardian. Review the new dosing instructions with the subject (application to only the target great toenail and to any other affected toenails) and provide a copy of new dosing instructions to the subject.
6. Dispense a new diary that includes the new dosing instructions.

Note: PK subjects who consented to only the 4 Week trial will exit the study on Day 29. Drug and subject diary will not be dispensed and urine pregnancy test will not be collected at this visit.

11.1.5 Schedule the PK subset subject (if consented to the 52-Week trial) for the next study visit. Visit 5 (Week 12 [\pm 5 days]), Visit S (Week 24 [\pm 5 days]), Visit 11 (Week 36 [\pm 5 days])

Visits are to be scheduled in reference to Visit 2 (Baseline).

The following procedures will be conducted at these visits:

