12.2 Assessment of Pharmacokinetics

The PK objectives will be considered met when approximately 16 evaluable subjects are treated under maximal use conditions through day 28 and PK samples collected at predose and 2, 4, 12 hrs postdose on Day 28 and 24 hrs postdose on Day 29.

No imputations will be made for missing data. Plasma concentrations that are reported as below the limit of quantitation (BLQ) in the data transfer file and will be set to zero for the summaries of concentrations as well as calculation of PK parameters. Missing values will be treated as if they were never drawn. Plasma concentrations and PK parameters will be summarized for the PK analysis set using descriptive statistics (n, mean, SD, standard error of the mean [SEM], coefficient of variation [CV], median, minimum, and maximum). Geometric means will also be used to summarize C_{max} , C_{min} , $AUC_{(0-t)}$ and $AUC_{(0-24h)}$.

Plasma concentrations of efinaconazole and metabolite (H3 and H4) at each scheduled sampling time point will be summarized using descriptive statistics. The individual plasma concentrations will be listed for each subject. Concentrations BLQ will be displayed as BLQ in the listings.

The mean plasma concentration time profiles for efinaconazole and metabolites (H3 and H4) will be presented graphically for Days 28 and 29 in both linear and logarithmic scales. Individual subject plasma concentration time profiles for efinaconazole and metabolites (H3 and H4) will also be created.

Plasma PK parameters for efinaconazole and metabolites (H3 and H4) will be calculated using noncompartmental analysis. The PK parameters will be calculated for each subject using actual sampling times. The maximum plasma concentration (C_{max}) and time to C_{max} (T_{max}) will be taken directly from the data.

The following PK parameters will be calculated from the individual plasma concentrations on Days 28 and 29 when possible:

- C_{max} (observed peak drug [efinaconazole and metabolites] concentration)
- T_{max} (time at which C_{max} occurs)
- C_{min} (observed minimum drug concentration)
- AUC_{0-t} (area under the concentration-time curve from time 0 up to the sampling time corresponding to the last quantifiable concentration)
- AUC_{0-24h} (area under the concentration-time curve from time 0 through 24 hours [corresponding to the dosing interval])

Additional PK parameters may be calculated as appropriate.

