12.8.1 Analysis Populations

All subjects who receive at least 1 confirmed dose of study drug will be included in the safety population.

All subjects in the PK subset who receive at least 1 confirmed dose of study drug and have any PK data on Days 28 and 29 will be included in the PK population.

All safety population subjects who are not in the PK subset will be included in the Non-PK population.

12.S.2 Sample Size Determination

Approximately 60 subjects will be enrolled and receive treatment with study drug.

Approximately 20 of the 60 subjects will be enrolled in the PK subset. These sample sizes were based on PK and clinical considerations; no formal sample size calculation was performed. The numbers of planned subjects are considered adequate for determining the safety profile and the PK parameters of efinaconazole in a pediatric population of subjects aged 6 to 16 years 11 months with mild to severe onychomycosis of the toenails.

12.S.3 Handling of Missing Data

No imputations will be made for analyses of safety or PK endpoints. The efficacy endpoints at Week 52, which are used to assess treatment compliance will have missing data imputed with the last observation carried forward (LOCF) for non-PK population analyses.

12.S.4 Multicenter Issues

The study will be conducted at multiple investigational centers in the US and the Caribbean with the intention of pooling the results for analysis.

12.S.5 Multiplicity Issues

Not applicable.

12.S.6 Windowing Rules

The timing of all study visits is relative to the Baseline (Day 1) visit. Visit 3 (Week 4) should occur within 5 days of Day 28, (except for the PK-subset; Visit 3 should occur within 1 day of Day 28) and Visit 3A (Week 4) should occur 1 day after Visit 3. The Week 8 and all subsequent visits should occur within 5 days of the targeted times.

13 Quality Control and Quality Assurance

This study will be conducted under the sponsorship of Valeant, in conformation with all appropriate local and federal regulations as well as ICH guidelines.

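### The maximal-use exposure summary is run on a PK population looser than the condition for meeting the PK objective, and the term evaluable is left undefined

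*Combined protocol and SAP*

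**What the plan says.** All references are to the latest protocol version in the file, the one that lets PK subjects choose a 4-week course.

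- **Who is analysed.** Section 12.8.1 and the synopsis admit PK-subset subjects "who receive at least 1 confirmed dose of study drug and have any PK data on Days 28 and 29". Neither adds an adherence criterion or a minimum number of samples.
- **What is reported on them.** Section 12.2: "Plasma concentrations and PK parameters will be summarized for the PK analysis set using descriptive statistics". Missing samples are treated as not drawn, and parameters are calculated where possible.
- **When the objective is met.** Section 12.2 requires that "approximately 16 evaluable subjects are treated under maximal use conditions through day 28 and PK samples collected at predose", and continues with 2, 4 and 12 h on Day 28 and 24 h on Day 29. The synopsis stops short of the samples: "approximately 16 evaluable subjects are treated under maximal use conditions through day 28 of the PK evaluation". Neither place says what makes a subject evaluable, and no summary restricted to evaluable subjects is planned.
- **How dosing is tracked.** Section 9.3 records missed-dose dates and bottle weights. Section 12.6 leaves the compliance calculation to the analysis plan and does not link it to the PK population.
- **Order of events at Visit 3 (Section 11.1.3).** Step 6 reads "Weigh the used bottle of the study drug". For PK subjects the next instruction that matters is "Collect a predose blood sample after all other study procedures are completed", and the clinic application follows that sample.

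**The concern.** The second primary objective is pharmacokinetics in 12 to 16 year olds, assessed under maximal use. Whether it has been met is judged on one group, and the exposure figures are produced on a wider one. A subject who skipped many home applications, or who has an incomplete profile, can enter the tables that will be read as maximal-use exposure.

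Such a summary is meant to show exposure at the upper end of use, so understatement is the direction that matters more. The amount applied for the profiled dose is also never recorded by weight. The used bottle is weighed before that application, PK subjects receive no bottle at Visit 3, and Visit 3A weighs only a newly dispensed one, which 4-week subjects do not receive.

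**Working it through.** **Inputs from the documents.** About 20 subjects in the PK subset, with no formal sample size calculation (Section 12.8.2). About 16 evaluable (Section 12.2). Five samples (20 mL in total at 4 mL each: 20/4 = 5). No dropout rate, variability or PK value is given, so there is no planned figure to reproduce. 16/20 = 80% is arithmetic on two approximate targets, not a stated expectation of loss.

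**Step 1: dilution of the mean.** Let *m* of 20 analysed subjects be non-evaluable, with exposure *r* relative to evaluable subjects. The arithmetic mean ratio is 1 − (*m*/20)(1 − *r*), and the geometric mean ratio is *r*^(*m*/20). Both are given because Section 12.2 plans both kinds of mean. The values of *r* are assumptions. Taking *m* = 4 uses the full gap between 20 and 16. Example: *m* = 4, *r* = 0.25 gives 1 − 0.20 × 0.75 = 0.85.

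| *m* | *r* | arithmetic | geometric |
|---|---|---|---|
| 4 | 0.25 | 0.85 | 0.76 |
| 4 | 0.50 | 0.90 | 0.87 |
| 4 | 0.75 | 0.95 | 0.94 |
| 2 | 0.25 | 0.925 | 0.87 |
| 2 | 0.50 | 0.95 | 0.93 |
| 2 | 0.75 | 0.975 | 0.97 |
| 0 | any | 1 | 1 |

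**Step 2: direction for missed doses.** An illustrative one-compartment model used the protocol's timing: daily doses on Days 1–26, none on the night before the visit, and the clinic dose on Day 28. Half-lives of 6–96 h and absorption rates of 0.1 or 0.7 per hour are assumptions. Ratios are to full adherence.

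- Half of the 26 earlier doses taken, on average: AUC 0.54–0.99, Cmax 0.55–0.99.
- None of the earlier doses taken: AUC 0.11–0.98.

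The direction is downward throughout. The amount depends on carry-over, which the documents do not let one judge.

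**Step 3: direction for missing samples.** Same model, full adherence, one postdose sample removed at a time.

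- 24 h missing: AUC0-t is 0.50–0.73 of the full value, because the area then ends at 12 h.
- 12 h missing: AUC is 0.87–1.17, so it can move either way. AUC0-t still runs to 24 h if that sample is quantifiable.
- Cmax is 0.87–1.00 whichever sample is lost.
- Cmin, a minimum over fewer values, can only stay the same or rise.
- Time-point means simply lose that subject, which carries no built-in direction, and AUC0-24h may not be calculated at all.

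**The case against.** The other side has several fair points.

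- **Section 12.2 does not define evaluable.** It states when the objective is met. A reader might infer that it sets a five-sample definition that the PK population contradicts. The text does not go that far; the defect is an undefined term together with a looser analysis set.
- **One sample may not be enough.** The phrase about data on Days 28 and 29 can be read as requiring data on both days. Either reading still falls short of five samples and neither requires adherence.
- **Partial profiles do not all lower exposure.** A reader might infer that they do. Step 3 supports that only for AUC0-t without the 24 h sample and, at most, for Cmax.
- **No loss of 4 is planned.** Subjects who leave before Day 28 have no PK data and are already outside the population, so using the full gap of 4 is an upper case, and the true number may be zero.
- **The SAP is a separate document.** Section 12.8 says so, and the change log refers to its wording. It may contain the missing rules.
- **Safeguards exist.** The Day 28 dose is applied at the center, so among doses after the first clinic application only the home doses are exposed to non-adherence. Individual concentrations are listed, profiles are plotted, and medians and maxima are reported. The analysis is descriptive.
- **A blanket five-sample rule would cost too much.** It would drop a fully adherent subject for one missed draw.

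All of this limits the size and scope of the point. None of it supplies a definition of evaluable or makes the summary set match the condition for success. Weighing around the clinic dose is a separate, lesser matter, since dosing is specified by coverage and not by weight.

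**Conclusion.** The mismatch is in the current text: the objective is judged on evaluable subjects under maximal use with five timed samples, exposure is summarised on a looser set, the key term is undefined, and the synopsis lacks the sample condition. The downward direction holds for doses missed before Day 28 (Cmax and AUC) and for AUC0-t without the 24 h sample. It is not a general property of incomplete profiles.

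The size cannot be taken from the documents. With 4 of 20 non-evaluable at an assumed 25–75% of evaluable exposure, the arithmetic mean is 5–15% low (geometric 6–24%). With 2, it is 2.5–7.5% low (geometric 3–13%). With none there is no effect. The conclusion is limited to the protocol text, because the SAP was not available for review.

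**What to change.** 1. Define evaluable before any concentrations are seen. Use an adherence criterion for Days 1–28, drawn from the diary and bottle weights already collected, and a minimum set of samples for each parameter (for example, a 24 h sample for AUC0-24h) in place of exclusion for any missing draw.
2. Base the primary maximal-use exposure summary on that set and keep the any-data PK population as a supportive summary beside it.
3. Align Section 12.8.1, Section 12.2 and the synopsis, and state whether PK data are needed on both days. If the SAP already holds such a rule, bring the protocol wording into line with it.
4. As a secondary step, weigh the bottle immediately before and after the Day 28 clinic application.

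The cost is wording in the protocol and, where needed, the SAP, plus two extra weighings per PK subject on equipment already in use. The downside is a slightly smaller n in the primary PK table. Fixing the rule in advance matters because exclusions chosen after seeing concentrations, in a set of about 20, would be open to challenge.

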Efinaconazole has successfully treated experimentally induced dermal candidiasis, *tinea corporis*, *tinea pedis*, and *tinea unguium* in vivo in guinea pig models. It has generally out performed reference drugs in these models, and in particular out performed the marketed drugs for *tinea unguium*: ciclopirox olamine (approved for the topical treatment of onychomycosis in the US), amorolfine (available outside the US as a topical nail lacquer), and terbinafine (available in the US in oral form).

The safety and efficacy of once daily use of efinaconazole for the treatment of onychomycosis of the toenail were assessed in two 52-week prospective, multicenter, randomized, double-blind

clinical studies. These studies were conducted in subjects 18 to 70 years of age with 20% to 50% clinical involvement of the target great toenail, without dermatophytomas or lunula (matrix) involvement (n = 870 in Study 1 and n = 781 in Study 2) [6]. These studies evaluated 48-weeks of treatment with efinaconazole relative to vehicle solution. At Week 52 (4-weeks after completion of therapy), efinaconazole was superior to vehicle solution in both studies and thus demonstrated efficacy in the treatment of onychomycosis. The most common adverse reactions (ie, reactions with incidences > 1%) reported in the studies were ingrown toenails, application site dermatitis, application site vesicles, and application site pain.

Efinaconazole was approved by the US Food and Drug Administration in June 2014 for the topical treatment of onychomycosis of the toenail(s) due to *T rubrum* and *T mentagrophytes* (Jublia® [efinaconazole] topical solution, 10% [6]). The approved drug is intended for topical application to affected toenails once daily for 48 weeks. During application, the toenail, toenail folds, toenail bed, hyponychium, and undersurface of the toenail plate are to be completely covered.

The current clinical study is designed to evaluate the safety and pharmacokinetics (PK) of once daily topical application of efinaconazole in the treatment of pediatric subjects with mild to severe onychomycosis of the toenails. Application and use of the study drug is consistent with the approved package insert. The evaluations included in the current study are consistent with the evaluations conducted in the development of the approved drug.

6 Study Objectives and Purpose

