7.2 Summary of Study Design

This is an open label, single-arm study designed to evaluate the safety and PK of a once daily topical application of efinaconazole in the treatment of pediatric subjects with mild to severe onychomycosis of the toenails. The study will include a total of 60 subjects, 40 of whom will be 6 to 16 years of age, inclusive, and PK assessments will be performed on approximately 20 subjects 12 to 16 years of age, inclusive (referred to throughout the protocol as the PK subset). All subjects must have onychomycosis of at least 1 great toenail; subjects in the PK subset must have onychomycosis of both great toenails and at least 4 other toenails. Efforts will be made to enroll subjects into the PK subset such that the subjects are evenly distributed across the required age range.

For subjects not participating in the PK subset, the study will consist of 14 scheduled visits, including Screening (up to Day -42), Baseline (Day 1), 12 treatment visits (Weeks 4, 8, 12, 16, 20, 24, 28, 32, 36, 40, 44, and 48), and a 4-week post-treatment follow-up visit (Week 52).

Subjects included in the PK subset MUST decide at time of consent whether to participate in the 4-Week trial, attend the scheduled visits up to Week 4 (Day 29) for collection of the final PK sample and exit the study OR participate in the 52-Week trial treatment through week 48 with additional visits at Weeks 8, 12, 16, 20, 24, 28, 32, 36, 40, 44, and 48), and a 4-week post-treatment follow-up visit (Week 52). The PK assessments will be performed under maximal use conditions.

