12.1.6 Efficacy for Assessing Treatment Compliance

This primary objective of this study is to assess the safety of the study drug. Descriptive efficacy statistics for the endpoints will assist in evaluating compliance with treatment for the purposes of safety assessment. The efficacy variables evaluated in this study include microscopic KOH examination and mycological culture outcomes of the target great toenail, percent involvement of the target great toenail, growth of the target great toenail, and assessments of the nontarget toenails. The efficacy endpoints include the following:

- Complete Cure, defined as 0% clinical involvement of the target toenail and negative KOH and fungal culture at Week 52
- Complete or Almost Complete Cure at Week 52, defined as :: 5% toenail involvement
- The Clinical Efficacy rate at Week 52, defined as an affected target great toenail area of < 10%
- The Mycologic Cure rate at Week 52, defined as a negative KOH examination and a negative fungal culture of the target great toenail sample

The Complete Cure rate, the Complete or Almost Complete Cure rate, the Clinical Efficacy rate, and the Mycologic Cure rate will be presented using descriptive statistics (sample size n, frequency counts, and percentages) for the safety, PK, and non-PK populations. In addition, the growth of the target great toenail at each study visit and the change from baseline in the number of affected nontarget toenails will be summarized descriptively.

A last observation carried forward (LOCF) imputation will be used to impute missing values for the efficacy variables at Week 52 for the non-PK population analyses. No sensitivity analyses will be conducted.

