12.8 Additional Statistical Considerations

All statistical processing will be performed using SAS® version 9.3 or higher unless otherwise stated. No hypothesis testing will be conducted in this study. A statistical analysis plan, describing all statistical analyses, will be provided as a separate document prior to data analysis.

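### Section 12.8.2 claims adequacy for PK at ages 6 to 16 although no child under 12 is sampled, and claims adequacy for safety without saying what event rate 40 or 60 subjects can detect or exclude

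*Combined protocol and SAP*

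**What the plan says.** All references are to the last amended version of the protocol in the combined file.

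- **Size and basis (12.8.2).** "Approximately 60 subjects will be enrolled and receive treatment with study drug", and "Approximately 20 of the 60 subjects will be enrolled in the PK subset". The numbers rest on PK and clinical considerations, and the section discloses that "no formal sample size calculation was performed". It then declares them adequate for the safety profile and for "the PK parameters of efinaconazole in a pediatric population of subjects aged 6 to 16 years 11 months". The sample size paragraph of the synopsis repeats the sentence.
- **Who gives PK samples (7.2).** "PK assessments will be performed on approximately 20 subjects 12 to 16 years of age, inclusive". The synopsis methodology, the PK objective in Section 6 and the PK subset criterion in Section 8.1 set the same lower age of 12.
- **Safety target (synopsis, Statistical Methods).** The primary safety objective counts as met once about 40 evaluable subjects have had 48 weeks of treatment.
- **Exposure of PK subjects (7.2 and 11.1.1).** They choose at consent between a 4-week and a 52-week participation. Those who choose 4 weeks cannot extend.
- **Adult background (Section 5).** Four reactions are named, introduced by "The most common adverse reactions (ie, reactions with incidences > 1" (a percentage). Individual rates are not given.
- **Reporting.** Section 12.1.1 summarizes treatment-emergent adverse events by number of subjects. Section 12.1.6 says the four Week 52 rates "will be presented using descriptive statistics (sample size n, frequency counts, and percentages". Neither section mentions a confidence interval. Section 12.8 adds: "No hypothesis testing will be conducted in this study".

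**The concern.** The adequacy sentence ascribes two properties to the design. The first, PK information across ages 6 to 16, contradicts the protocol's own sampling plan. A reader of the report could take adolescent PK results as covering younger children because the protocol said the numbers sufficed for them.

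The second, adequacy for the safety profile, cannot be checked as written. Safety is a primary objective of a single-arm study, so the useful question is which event rates the study could reveal or rule out. The protocol gives no such figure, and the reporting it describes is limited to counts and percentages. A table entry of zero then has no stated bound.

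**Working it through.** **There is no plan figure to reproduce.** No alpha, power, event rate or precision is stated. The check is therefore of the claim, not of the number 60.

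**PK by age.** Claimed range: 6 to 16 years 11 months (12.8.2 and synopsis). Sampled range: 12 to 16 (synopsis methodology, Sections 6, 7.2 and 8.1). Subjects aged 6 to 11 with PK samples: 0 of about 20. Enlarging the subset would not change this, because the lower bound is an eligibility criterion.

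**Inputs for safety.** n = 40 is the synopsis target for 48-week treatment; n = 60 is the total enrolled. If all of the roughly 20 PK subjects chose the 4-week option, 60 − 20 = 40 would remain for 48-week exposure before any dropout. The figures for n = 60 are thus a best case.

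**Exclusion limit after zero events**, exact two-sided 95%: 1 − 0.025^(1/n).
- n = 40: 1 − 0.025^(1/40) = 8.8%
- n = 60: 1 − 0.025^(1/60) = 6.0%

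**Rate with a 95% chance of at least one case**: 1 − 0.05^(1/n). This is also the one-sided 95% upper bound after zero events.
- n = 40: 7.2%
- n = 60: 4.9%

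**Chance of seeing no case of a given reaction** with true rate p: (1 − p)^n. The protocol gives only a floor of 1%, so the range 1% to 3% is my assumption, and it supposes that children react at such rates.

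| True rate | n = 40 | n = 60 |
|---|---|---|
| 1% (the floor) | 66.9% | 54.7% |
| 1.5% | 54.6% | 40.4% |
| 2% | 44.6% | 29.8% |
| 3% | 29.6% | 16.1% |

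**Where missing and seeing are equally likely**: 1 − 0.5^(1/n) = 1.72% for n = 40 and 1.15% for n = 60.

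The exclusion and detection limits depend on n alone. Only the table rests on the assumed rates.

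**The case against.** The strongest reply is that this is a disclosed convenience sample in a descriptive study. The protocol admits that no calculation was made, tests nothing, and never claims to detect 1% events. That stands against any charge of a miscalculated sample size, and none is made here. It does not support a positive statement of adequacy.

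A reader might go further and infer that 40 to 60 children will usually miss the common adult reactions. The documents do not support that. One percent is the lower bound of the list, not the rate of any named reaction, and missing is the likelier outcome only below 1.72% (n=40) or 1.15% (n=60). The figures are also per reaction. With four independent reactions at 1% each, the chance of at least one case of any of them is 1 − 0.99^160 = 80% for n = 40 and 1 − 0.99^240 = 91% for n = 60. That is fair, but seeing some reaction does not bound the rate of another that was not seen.

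Section 11.2.1 solicits redness, swelling, burning, itching and vesication at each follow-up visit through Week 52. This improves ascertainment of local events. It does not move the binomial limits, and ingrown toenail, one of the named adult reactions, is not on the solicited list.

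On PK, it can be said that the sentence merely names the whole study population once for both aims, and that every operational section has the right age range. This is true. No enrolment or sampling step is affected, but the sentence as it stands is still wrong.

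Finally, Section 12.8 refers the analyses to a separate analysis plan whose text is not in the file reviewed. It would be too strong to infer that the results will carry no intervals. What can be said is that the protocol plans none. The counts-and-percentages wording in 12.1.6 concerns the Week 52 rates only; for adverse events the relevant section is 12.1.1.

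**Conclusion.** The point holds in two parts.

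The PK part rests on a direct comparison of sections and needs no assumption: adequacy is claimed for ages 6 to 16 years 11 months, and the design provides no PK data at ages 6 to 11.

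The safety part is an unsupported statement, not an error in the number. The exclusion limits of 8.8% and 6.0% are exact for their n, under independent subjects with a common event rate. The miss probabilities of 67% to 30% (n=40) and 55% to 16% (n=60) are conditional on the assumed 1% to 3% range.

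This should be corrected because it governs how zero or few events will be read. It is no reason to enlarge the study or change its conduct.

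**What to change.** 1. In Section 12.8.2 and in the sample size paragraph of the synopsis, limit the PK claim to ages 12 to 16 years 11 months. Changing only one place would create a new inconsistency.
2. In the same two places, replace the bare safety claim with the limits. With 40 subjects treated for 48 weeks, a reaction occurring in 7.2% has a 95% chance of appearing at least once, and zero cases give an exact two-sided 95% upper limit of 8.8%. With 60 subjects the figures are 4.9% and 6.0%. State that 60 overstates 48-week exposure if PK subjects take the 4-week option. If the adult reactions are cited, label any rate as assumed and show a range.
3. Add exact (Clopper-Pearson) 95% confidence intervals to the incidence of treatment-emergent adverse events in Section 12.1.1 and, optionally, to the four Week 52 rates in Section 12.1.6. Intervals are descriptive and are compatible with the absence of hypothesis tests. If the separate analysis plan already has them, a cross-reference is enough.

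The cost is a few sentences, one option in the table programs, slightly longer tables and a less favourable stated claim.
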